5.9. Missing Data

Missing data will not be imputed unless specified otherwise. Missing eCRF data due to Covid-19 will be listed.

This document is confidential.

6. Demographic, Other Baseline Characteristics and Medication

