been previously withdrawn from study drug for those patients who have been withdrawn from study drug.

- Change in health questionnaires to end of treatment period 3 and 6:
 - Health Assessment Questionnaire-Disability Index (HAQ-DI)
 - The Provider Global Assessment of Disease Activity (PrGA)
 - Short Form Health Survey 36 (SF-36)
- Percent of patients on SEL-212 vs. KRYSTEXXA® of gout flare incidence per 3-month period (Treatment Periods 1-3 and Treatment Periods 4-6)
- Percent of patients on SEL-212 vs. KRYSTEXXA® of gout flare frequency per 3-month period (Treatment Periods 1-3 and Treatment Periods 4-6)
- Change from Baseline to Treatment Period 6 in number of tender joints
- Change from Baseline to Treatment Period 6 in number of swollen joints

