7.2.2. Change from baseline in HAQ-DI Total Score

The HAQ-DI, which includes the patient global assessment and pain scale, is an instrument that assesses fine movements of the upper extremity, locomotor activities of the lower extremity, and activities that involve both the upper and lower extremities. Standard scoring takes into account the use of aids and devices or assistance from another person. There are 20 items in 8 categories that represent a comprehensive set of functional activities: dressing, rising, eating, walking, hygiene, reach, grip, and usual activities. The stem of each item assesses a patient's functional ability using their usual equipment during the past week. Each category contains at least 2 specific sub-category questions. For example, under the category "walking," patients are asked about their ability to walk outdoors on flat ground and to climb up 5 steps.

Eight (8) categories will be assessed by the HAQ-DI: 1) dressing and grooming, 2) arising, 3) eating, 4) walking, 5) hygiene, 6) reaching, 7) gripping, and 8) common daily activities. There are 2 or 3 questions for each section. Scoring within each section is on a 4-point Likert scale from 0 (without any difficulty) to 3 (unable to do). The score given to each section is the worst (highest) score within the section (ie, if one question is scored 1 and another 2, then the score for the section is 2). In addition, if an aid or device is used or if help is required from another individual, then the minimum score for that section is 2. If the section score is already 2 or more then no modification is made. The sum of the 8 scores of the 8 sections will be divided by 8 to obtain the HAQ-DI total score. In the event that one section is not completed by a subject then the summed score would be divided by 7. The HAQ-DI total score will be calculated if 6 or more sections are available.

Comparison with regards to change from baseline will be performed using an ANCOVA with the respective change from baseline value as dependent variable, treatment group and the randomization stratum as independent fixed factors and the baseline value as independent covariate.

Summary tables of total scores will be provided for each scheduled assessment time by treatment group. Additionally, summaries of the changes from baseline will be provided.

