7.2.5. Gout Flares Incidence and Frequency

The number and percentage of patients reporting gout flares per 3-months period and overall, i.e. Treatment Periods 1-3, Treatment Periods 4-6 and Periods 1-6, will be summarized by treatment group and will be tested using a CMH-test considering the randomization stratum. The same analysis will also be performed by patient's maximum severity of gout flare experienced within each 3-months period.

The frequency of gout flares will be summarized per 3-months period and overall and by severity for each treatment group and will be compared using ANOVA model with presence of tophus and treatment group as fixed factors. In addition for periods 4-6 and 1-6, poisson regression model will be used with number of gout flares as independent variable, treatment and presence of tophus as fixed factor, and length of follow-up for each corresponding treatment period as covariate.

7.2.6. Change from Baseline to Treatment Period 6 in Number of Tender and Swollen Joints

Comparison with regards to change in number of tender joints from baseline to end of treatment period 3 (day 0 period 4) and period 6 will be performed using an ANCOVA with the change from baseline value as dependent variable, treatment group and randomization stratum as independent fixed factors and the baseline number of tender joints as independent covariate. In case of non-normality the non-parametric Wilcoxon test will be used for the comparison between the treatment groups. Summary tables of the number of tender joints for each assessment time point and for the change from baseline will be provided by treatment group.

Comparison with regards to change of swollen joints from baseline to end of treatment period 3 (day 0 period 4) and 6 will be performed using an ANCOVA with the change from baseline value as dependent variable, treatment group and randomization stratum as independent fixed factors and the baseline number of swollen joints as independent covariate. In case of non-normality, the non-parametric Wilcoxon test will be used for the comparison between the treatment groups. Summary tables of the number of

This document is confidential.

swollen joints for each assessment time point and for the change from baseline will be provided by treatment group.

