7.4. Deviation from Analyses Planned in Protocol

7.4.1. Additional analyses

The following analyses are added even though they are not included in the protocol:

- Interim analysis.
- Subgroup analyses on the secondary endpoint by patient's primary efficacy endpoint (responder vs. non-responder).

The following analyses have been added as a result of the impact of Covid-19 on the study which may result in a larger anticipated number of subjects not completing the study and therefore not undergoing the assessments required for the primary efficacy endpoint or the study being stopped prematurely by sponsor decision. This is in line with FDA Guidance on Conduct of Clinical Trials of Medical Products during COVID-19 Pandemic Guidance for Industry, Investigators, and Institutional Review Boards.

- Additional analyses suggested to primary endpoint as sensitivity analyses to determine if the impact that these have on the conclusions of the study and to describe the impact of Covid-19 on the study performance.
- A sensitivity analysis which limited the analysis to results processed in the central laboratory to determine if this resulted in different conclusions to those found from the full analysis to determine consistency in laboratory testing between central and local laboratories.
- Kaplan-Meier analysis of withdrawal from study by treatment arm and presence of tophus to determine if subjects withdraw from the study in different proportions and at different rates within the treatment groups and depending on the presence of tophus.
- Kaplan-Meier analysis of withdrawal from study due to an adverse event by treatment arm and presence of tophus to determine if subjects experience adverse events in different proportions and at different rates within the treatment groups and depending on the presence of tophus.
- Poisson regression with number of gout flares experienced during treatment periods 1-6 as the dependent variable, treatment and the presence of tophus as independent variables and length of follow up as a covariate. The ITT population would be used to conduct this analysis. Similar analysis is done for periods 4-6.

This document is confidential.

8. Safety

The population used for safety analyses will be the Safety Set (SS). Safety will be assessed on the basis of adverse event (AE), clinical laboratory data, ECG parameters, physical examinations, and vital signs.

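### The Month 6 questionnaire and joint-count comparisons carry an ITT label but are complete-case analyses that leave out the Month 3 value of later dropouts

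*SAP*

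**What the plan says.** - **General rule.** SAP section 5.9: "Missing data will not be imputed unless specified otherwise". A missed visit is imputed only for SUA (SAP section 7.1). The one rule inside a questionnaire section, "The HAQ-DI total score will be calculated if 6 or more sections are available" (SAP section 7.2.2), deals with unanswered sections of a completed form.
- **Model.** The HAQ-DI analysis is an "ANCOVA with the respective change from baseline value as dependent variable, treatment group and the randomization stratum as independent fixed factors", with the baseline value as covariate. PrGA, SF-36 and the joint counts have the same form (SAP sections 7.2.3, 7.2.4, 7.2.6). None has a visit term or repeated measures.
- **Time points.** SAP section 4.2 lists "Change in health questionnaires to end of treatment period 3 and 6". SAP section 7.2.6 compares "change in number of tender joints from baseline to end of treatment period 3 (day 0 period 4) and period 6", and likewise swollen joints. Its fallback is: "In case of non-normality the non-parametric Wilcoxon test will be used for the comparison between the treatment groups".
- **Analysis set.** Protocol section 13.4.2 puts the secondary analyses on the ITT and PP Sets, and ITT is all randomized patients (SAP section 5.3). SAP sections 7.2.2 to 7.2.6 name no set.
- **Schedule.** Both measures are taken at Treatment Period (TP) 1 Day 0, TP4 Day 0, TP6 Day 28 and Early Termination (Protocol Appendices A and C). The SAP does not say how Early Termination values are used.
- **Follow-up.** Patients withdrawn from study drug continue visits to the end of TP6 (Protocol sections 7.4.1.1 and 7.4.1.2). SAP section 7.4.1 says Covid-19 may lead to "a larger anticipated number of subjects not completing the study".

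**The concern.** A patient seen at TP4 Day 0 but not at TP6 Day 28 drops out of the TP6 model. The model then estimates the treatment difference among those who stayed, not among all randomized. That is harmless if leaving depends only on treatment, stratum and baseline. If patients doing worse at Month 3 are likelier to leave, and the extent of leaving differs by arm, the TP6 difference is biased, even though the Month 3 value that would correct it has been collected.

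The missing-data sensitivity analyses promised in Protocol section 13.4.1 and set out in SAP section 7.1 concern the primary endpoint, so nothing planned would show the problem for these endpoints. Because the use of Early Termination values is undefined, two programmers could also produce different TP6 results from the same data.

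**Working it through.** **The plan's own figure.** The documents give no effect, SD or dropout rate for these endpoints. The only calculable figure is the primary sample size: 65% vs 44%, one-sided 5%, power 80%. With pooled rate 0.545:

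n = [1.645 × √(2 × 0.545 × 0.455) + 0.842 × √(0.65 × 0.35 + 0.44 × 0.56)]² / 0.21² = 68.5, so 69 per arm, as stated. Randomizing 75 leaves room for 1 − 69/75 = 8% loss. Only the 75 per arm is used below.

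**Assumed inputs (none is in the documents).** SD 1; lower score better (the sign reverses for SF-36); correlation 0.5 of baseline with each later visit and 0.7 between Month 3 and Month 6; dropout before Month 6 of 10 to 30% per arm; log-odds of dropout rising by 0, 0.5 or 1 per SD of a worse Month 3 value.

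**Where the bias comes from.** The Month 6 slope on Month 3, given baseline, is (0.7 − 0.5 × 0.5) / (1 − 0.5²) = 0.6. The complete-case bias is 0.6 times the distortion, among completers, of the baseline-adjusted arm difference at Month 3. A bias of 0.08 SD therefore needs a distortion of 0.08 / 0.6 = 0.13 SD. With no arm difference in selection, it is 0.

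**Simulated estimates (75 per arm, 4,000 trials per row, slope 1, true effect −0.40 SD).**

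| Missing, SEL-212 / KRYSTEXXA | Complete-case | Using Month 3 | Complete-case bias |
|---|---|---|---|
| 20% / 20% | −0.399 | −0.399 | about 0 |
| 15% / 25% | −0.364 | −0.400 | +0.04 |
| 10% / 30% | −0.321 | −0.397 | +0.08 |
| 30% / 10% | −0.474 | −0.401 | −0.07 |

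Positive bias understates SEL-212 and negative bias overstates it. Simulation error is about 0.157 / √4000 = 0.0025.

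- At 15% / 30% missing with no true effect, the bias is 0.057 SD at slope 1, 0.034 at slope 0.5 and about 0 at slope 0.
- With no true effect, the nominal 5% one-sided test favours SEL-212 in 1.7% of trials at 10% / 30% and 10.7% at 30% / 10%.

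**Precision.** At 20% missing in both arms, unrelated to outcome:
- Complete-case standard error: √(2/60 × 0.75) = 0.158.
- Using Month 3: the residual variance given baseline and Month 3 is 0.75 × (1 − 0.6²) = 0.48, so √(2/60 × 0.48 + 0.6² × 0.75 × 2/75) = √(0.0160 + 0.0072) = 0.152, which is 3.7% smaller.
- Simulation gives 0.161 against 0.155. Across scenarios the gain is about 2 to 4%.

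**What the repeated-measures model cannot recover.** At 15% / 30% and slope 1, if half the dropouts also lack Month 3, a bias of about 0.025 SD remains. If all lack it, the whole bias remains.

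**The case against.** The case for leaving the plan alone is substantial.

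- **Stopping-rule failures are not lost by design.** They are the most obvious outcome-related loss that could differ by arm, but they stay in visits to the end of TP6. Protocol section 8.2.1.3.1 also discourages investigators from terminating dosed patients. This stands and narrows the problem. It does not close it, because the PP definition (SAP section 5.5) itself provides for leaving the study after stopping rules, adverse events or investigator discretion.
- **Covid-19.** A reader might infer that the SAP predicts heavy or unequal dropout. It does not: it says the pandemic may raise non-completion, gives no rate or arm difference, and is discussing the primary endpoint assessments. Disruption unrelated to the patient's condition costs precision, not validity.
- **Month 3 data.** A reader might infer that they are discarded. They have their own planned comparison and are unused only in the TP6 contrast.
- **Withdrawal is examined.** SAP section 6.1 plans Kaplan-Meier curves and log-rank tests by arm. These would reveal unequal withdrawal but would not adjust the TP6 comparison.
- **Size.** Even 0.08 SD is half a standard error, and the precision gain is small. Both points stand.

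**Conclusion.** The gap is real and moderate. As written, the TP6 comparisons of HAQ-DI, PrGA, SF-36 and joint counts are complete-case analyses under an ITT label, and the handling of Early Termination values is undefined. The bias is 0 with equal dropout or dropout unrelated to outcome, and reaches about 0.08 SD at 10% against 30% with strong dependence on Month 3, against a standard error of about 0.16. Every input to that range is an assumption. The documents do not support a claim that these results will be biased, nor any particular size or direction. Nor do they support extending the point to the primary result: these endpoints are secondary, and SAP section 7.2 gives them no hierarchical order. The unknown direction is the reason to settle the method before the data are seen.

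**What to change.** - Report the TP6 comparison as the TP6 contrast from one mixed model for repeated measures per endpoint: treatment by visit, baseline by visit, tophus stratum, unstructured covariance, with visits TP4 Day 0 and TP6 Day 28.
- Use an Early Termination value only when it falls within the window of a scheduled visit. Do not carry it forward to TP6.
- For joint counts, keep the Wilcoxon test as a sensitivity analysis in place of its role as a fallback.
- Report the numbers analysed by arm and visit, so that the distance from the full ITT Set is visible.

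The cost is SAP wording and programming; no new data are needed. The model relies on data being missing at random given treatment, stratum, baseline and Month 3. This is weaker than what the single-visit ANCOVA assumes, but still untestable. Patients with no post-baseline value remain outside the treatment contrast.

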6.1. Patient Disposition and Withdrawals

Patient disposition data will be listed. Summary tables reflecting the number of patients for the following will be presented:

- Screened (or Enrolled) patients
- ITT, SS, mITT, and PP patients
- Patients who complete the study treatment
- Patients who early terminate the study treatment and reasons for early termination
- Patients who early terminate the study and reasons for early termination

Screen Failure patients will be listed.

Kaplan-Meier (KM) figures of the time to early termination of the study by treatment group and by presence of tophus will be provided.

Kaplan-Meier (KM) figures of the time to early termination of the study due to adverse event by treatment group and by presence of tophus will be provided.

Kaplan-Meier (KM) figures of the time to early study treatment discontinuation by treatment group and by presence of tophus will be provided.

Kaplan-Meier (KM) figures of the time to early study treatment discontinuation due to stopping rules by treatment group and by presence of tophus will be provided.

Kaplan-Meier (KM) figures of the time to early study treatment discontinuation due to stopping rules or due to Infusion-related reactions including infusion reaction, allergic reaction to pre-med or one of drug components and anaphylaxis, by treatment group and by presence of tophus will be provided.

In addition, stratified Log-rank test will be used to test treatment difference with presence of tophus as stratification factor for those time to event endpoint mentioned above. Unstratified Log-rank test will be used to test treatment difference for patients with presence of tophus and for patients with absence of tophus.

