5.5 Approved Therapies for Chronic Gout Refractory to Conventional Therapy

An estimated 160,000 gout patients fail to normalize their levels of SUA, have symptoms that are uncontrolled with the currently available treatments aimed at lowering urate levels, or suffer from comorbidities that preclude their use of conventional therapies (*Richette 2013, Strand 2012*). Lack of treatment options leads to unabated disease progression.

Currently, conventional therapies for the treatment of gout involve the inhibition of uric acid production and the improvement of uric acid renal clearance. The administration of exogenous uricase, an enzyme not present in humans that converts uric acid into the water-soluble compound, allantoin, is used only in instances of gout that is refractory to first and second lines of therapy (*Dalbeth 2011*).

There are 2 uricase products currently used to treat hyperuricemia: rasburicase (ELITEK®) and pegloticase (Krystexxa®).

Rasburicase is a recombinant, unpegylated urate-oxidase enzyme produced by genetically modified *S. cerevisiae*. It is indicated for tumor lysis syndrome, and its use in treating gout is off-label. Its clinical use in gout is limited because it is highly immunogenic and has a short plasma half-life at approximately 18 to 24 hours, making it an unsuitable treatment for chronic refractory gout ([Terkeltaub 2009](#)).

Pegloticase is a pegylated recombinant porcine- or baboon-derived uricase. It is currently the only FDA-approved product for the treatment of chronic gout refractory to conventional therapy ([KRYSTEXXA Prescribing Information 2018](#)). While its use is associated with improvements in musculoskeletal function, quality of life, and pain, only approximately 42% of patients maintain a target serum urate level less than 6 mg/dL after 6 months of the approved dose regimen of 8 mg once every 2 weeks. The vast majority of patients (92%) develop anti-pegloticase antibodies. High titer antibodies appear to adversely affect the pharmacokinetics and pharmacodynamics of the enzyme and are associated with a decrease in therapeutic response and increased risk of infusion reactions. Approximately 26% of patients taking Krystexxa report infusion reactions, 6.5% experience anaphylaxis, and the incidence of infusion reactions correlate with high anti-pegloticase antibody titer. These adverse events are typically preceded by a loss of urate-lowering effects.

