8.2.1.3 Enrolled Patient Withdrawal and Discontinuations

8.2.1.3.1 Withdrawal Procedures

Early termination from the study occurs when an enrolled patient withdraws consent or the Investigator terminates a patient. The reason for withdrawal will be evaluated and recorded in the case report form (CRF) and source documents. Patients that withdraw will not be replaced.

Patients may withdraw consent at any time. Reason(s) for withdrawal of consent, failure to return for the necessary visits, or termination from the study should be documented. All patients that withdraw early from the study, upon termination should have the Early Termination visit

assessments completed (i.e., End of Study assessments) ([Section 20](#)), if the assessments pose no risk to the patient and the patient allows such assessments.

The Investigator should consult with the Sponsor/medical monitor prior to withdrawing any patient from the study. Since this is a multiple-dose study, once dosed, patients generally should not be terminated by the Investigator and should be followed through the end of Treatment Period 6, unless the patient withdraws consent or is lost to follow-up. In situations where continued participation in certain aspects of the study pose a risk to the patient, with consultation with the medical monitor, the Investigator should discontinue those procedures that pose a risk and should continue to collect data and conduct those assessments that do not put the patient at risk through the end of Treatment Period 6. Patients with compliance issues or major deviations that effect data quality will also continue to be followed through the end of Treatment Period 6 collecting as much data on the patient as possible, unless otherwise indicated by the Sponsor.

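### The SAP's adverse-event curve counts exits from the study rather than stops of study drug, and its cause-specific Kaplan-Meier curves leave competing stops undefined

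*SAP*

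**What the plan says.** SAP 6.1 lists five Kaplan-Meier figures, each by arm and by tophus presence:

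1. exit from the study, any cause;
2. exit from the study because of an adverse event: "Kaplan-Meier (KM) figures of the time to early termination of the study due to adverse event by treatment group";
3. stop of study treatment, any cause;
4. stop of study treatment for the stopping rules alone: "Kaplan-Meier (KM) figures of the time to early study treatment discontinuation due to stopping rules by treatment group";
5. a composite: "discontinuation due to stopping rules or due to Infusion-related reactions including infusion reaction, allergic reaction to pre-med", with reactions to a drug component and anaphylaxis also included.

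For testing, a "stratified Log-rank test will be used to test treatment difference with presence of tophus as stratification factor for those time to event endpoint mentioned above", followed by unstratified log-rank tests within each tophus stratum. SAP 7.4.1 explains that figure 2 was added "to determine if subjects experience adverse events in different proportions and at different rates within the treatment groups".

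Protocol 8.2.1.3.1 says that "once dosed, patients generally should not be terminated by the Investigator and should be followed through the end of Treatment Period 6". The exceptions are withdrawal of consent and loss to follow-up. Where a procedure poses a risk, that procedure is dropped and data collection goes on. Protocol 7.4.1.1 and 7.4.1.2 likewise keep patients withdrawn from drug on study visits to the end of Treatment Period 6.

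SAP 6.1 states no censoring rule, time origin or analysis set for these curves, and no alpha or sidedness for the tests.

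**The concern.** There are two separate faults, and they fall on different curves.

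**The event does not match the question (figure 2).** The stated aim is to compare adverse-event experience. The event counted is leaving the study, which the protocol tells sites generally to avoid. The better the sites comply, the fewer adverse-event-driven stops the curve records. A non-significant log-rank test on a few exits could be read as evidence of similar tolerability.

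**Competing reasons for stopping (mainly figure 4).** A patient already off drug for another reason can no longer stop because of a stopping rule. If such patients are censored, the usual Kaplan-Meier default, one minus the curve is higher than the proportion who actually stopped for that reason. The excess grows with the amount of competing stopping, so unequal competing stops can alter or create a visible gap between arms.

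**Working it through.** **The plan's own figure.** The documents give no event count, rate or power for these curves. The only design figure is 69 per arm for the primary endpoint (Protocol 13.1: 65% v 44%, one-sided 5%, power 80%). It reproduces: [1.645·√(2·0.545·0.455) + 0.842·√(0.65·0.35 + 0.44·0.56)]² / 0.21² = 68.5, rounded up to 69. It does not bear on SAP 6.1. Every rate below is an assumption.

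**Step 1: which patients are events in which curve?**

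| Patient | Study exit due to AE (2) | Drug stop, any cause (3) | Stopping rules (4) | Composite (5) |
|---|---|---|---|---|
| Stops drug for an infusion reaction, stays on visits | no | yes | no | yes |
| Stops drug for another AE, stays on visits | no | yes | no | no |
| Stops drug under a stopping rule, stays on visits | no | yes | yes | yes |
| Leaves the study because of an AE, having stopped drug for it (not an infusion reaction) | yes | yes | no | no |

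No column isolates drug discontinuation due to any adverse event. In the second row, the only curve that counts the patient is the all-cause one.

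**Step 2: how informative could figure 2 be?** Assume 2–5% of 150 patients leave the study for an adverse event: 150 × 0.02 = 3 to 150 × 0.05 = 7.5 events. Log-rank power at one-sided 5% (assumed) with D events is Φ(½·√D·|ln HR| − 1.645). For a hazard ratio of 0.5:

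- D = 2: 12%
- D = 4: 17%
- D = 8: 25%
- 80% power needs D = 52

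If every event fell in one arm, at least five would be needed for significance (0.5⁴ = 0.0625; 0.5⁵ = 0.031). The tests within tophus strata split these events further.

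**Step 3: size of the Kaplan-Meier excess in figure 4.** Let F₁ be the true cumulative incidence of stopping-rule stops and F₂ that of other stops. With proportional cause-specific hazards, H = −ln(1 − F₁ − F₂), and 1 − KM = 1 − exp[−H·F₁/(F₁ + F₂)].

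Worked case, F₁ = 0.35 and F₂ = 0.25: H = −ln 0.40 = 0.916; 0.916 × 0.35/0.60 = 0.534; 1 − e^(−0.534) = 0.414.

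| F₁ | F₂ | 1 − KM | Excess (points) |
|---|---|---|---|
| 35% | 5% | 36.0% | 1.0 |
| 35% | 10% | 37.2% | 2.2 |
| 35% | 15% | 38.4% | 3.4 |
| 35% | 25% | 41.4% | 6.4 |

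Over F₁ of 20–50% and F₂ of 5–30% the excess runs from 0.6 to 13.4 points. Timing matters too. With F₁ = 35% and F₂ = 25%, 1 − KM is 35% if all competing stops come last, and 0.35/0.75 = 46.7% if all come first.

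Two arms that both have a true 35%, with competing stops of 5% and 25%, would show 36.0% and 41.4%: a false gap of 5.4 points.

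**Step 4: the same check on figure 2.** A true 5% with 15% competing exits reads 5.4%; with 30% it reads 6.0%. Overstatement is negligible there. Figure 2's fault is the event definition.

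**Step 5: could competing stops be appreciable or unequal?** Protocol 5.5 reports infusion reactions in about 26% of pegloticase patients and anaphylaxis in 6.5%, though not every reaction ends treatment. Protocol 7.4.1.1 also withdraws SEL-212 patients from drug when the Day 21 value is missing and no later value qualifies them. The per-protocol definition mentions discontinuation at the investigator's discretion in the KRYSTEXXA arm. So the documents foresee other routes off drug that differ by arm, but give no rates.

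**The case against.** **Much of the gap is already covered.** SAP 6.1 tabulates reasons for stopping treatment and plans an all-cause treatment-discontinuation curve. Figure 5 counts infusion-related reactions as events. SAP 8.1 gives stopping-rule counts and percentages with a CMH test, and SAP 8.3 summarises adverse events leading to drug withdrawal. This stands: adverse-event discontinuations are reported. What is missing is their timing, and a comparison of the arms on that event.

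**Study exit matters in its own right.** SAP 7.4.1 added the exit curves because of Covid-19 dropout, and SAP 7.1 makes anyone who leaves before completing Period 6 a non-responder. This stands, and it is why the curve should be kept and not replaced.

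Four stronger readings are tempting and are not supported:

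- *Figure 2 will be near-empty.* No event rate is given. Patients may withdraw consent because of an adverse event, and the per-protocol definition foresees study exits after such events. Sparse is likely; empty is not shown.
- *The SAP censors competing stops.* The SAP is silent. Censoring is the usual default, so the demonstrable fault is an unstated rule.
- *The tests are invalid.* With other stops censored, the log-rank test validly compares cause-specific hazards. The overstatement arises only when one minus Kaplan-Meier is read as a probability, and the SAP specifies no such percentages.
- *Censoring is shown to be informative in both arms.* Protocol 5.5 says "These adverse events are typically preceded by a loss of urate-lowering effects", but this describes pegloticase alone and gives no evidence about SEL-212.

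**Conclusion.** The point holds, with minor severity. The event in figure 2 does not match the purpose in SAP 7.4.1, and this follows from the documents with no assumed number. No planned time-to-event analysis covers study-drug discontinuation due to any adverse event.

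The second fault is conditional on competing stops being censored. At a true 35% the stopping-rule curve would then read about 1 to 2 points too high with 5–10% competing stops and about 6 points with 25%. Equal incidence with 5% v 25% competing stops would show a false gap of about 5 points. These sizes rest on assumed rates and proportional cause-specific hazards.

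A reader might infer that the tolerability results as a whole are unreliable. The documents do not support that: the all-cause curves, the crude counts in SAP 6.1, 8.1 and 8.3, and the primary CMH test are untouched.

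**What to change.** In SAP 6.1 and 7.4.1:

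- Add time to permanent discontinuation of study drug due to adverse event, by arm and tophus stratum, as the tolerability curve. Take the event from the recorded reason for stopping treatment, because the drug-withdrawn category in Protocol 12.2.2.5 describes ending an infusion.
- Keep study exit due to adverse event as a descriptive check on Covid-19 dropout, and reword its purpose accordingly.
- For cause-specific events (adverse event; stopping rules; stopping rules or infusion-related reactions), show Aalen-Johansen cumulative incidence, with other reasons for stopping as competing events.
- Keep Kaplan-Meier for the two all-cause curves. Label the log-rank test on any cause-specific event as a comparison of cause-specific hazards.
- State the censoring rule, time origin, analysis set and sidedness.

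The cost is SAP wording and a little extra programming. The reasons for stopping are already collected, so no new data are needed.
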